3.3.2 Dose intensity

Relative dose intensity (RDI) is the percentage of the actual dose delivered relative to the intended dose through to treatment discontinuation. RDI will be defined as follows:

- $\text{RDI} = 100\% \times d/D$, where d is the actual cumulative dose delivered up to the actual last day of dosing and D is the intended cumulative dose up to the actual last day of dosing. D is the total dose that would be delivered, if there were no modification to dose or schedule.

3.3.3 Adverse events (AEs)

Adverse events and serious adverse events (SAEs) will be collected throughout the study, from date of informed consent until 28 days after the last dose of study treatment (or end of follow-up period). Events will be defined as treatment emergent if they onset or worsen (by investigator report of a change in intensity), during the treatment period as defined in the protocol. The Medical Dictionary for Regulatory Activities (MedDRA) (using the latest or current MedDRA version) will be used to code the AEs. AEs will be graded according to the National Cancer Institute Common Terminology Criteria for AEs (using the CTCAE version referenced in the Clinical Study Protocol).

Other significant adverse events (OAEs)

During the evaluation of the AE data, an AstraZeneca medically qualified expert will review the list of AEs that were not reported as SAEs and ‘Discontinuation of Investigational Product due to Adverse Events’ (DAEs). Based on the expert’s judgement, significant adverse events of particular clinical importance may, after consultation with the Global Patient Safety Physician, be considered other significant adverse events (OAEs) and reported as such in the CSR. A similar review of laboratory/vital signs/ECG data will be performed for identification of OAEs.

Examples of these are marked haematological and other laboratory abnormalities, and certain events that lead to intervention (other than those already classified as serious) or significant additional treatment.

AEs of special interest

Some clinical concepts (including some selected individual preferred terms and higher-level terms) have been considered “AEs of special interest” (AESI). AESIs represent pre-specified risks that are considered to be of importance to a clinical development program.

These AESIs have been identified as a list of categories provided by the patient safety team.

Other categories may be added as necessary or existing terms may be merged. An AstraZeneca medically qualified expert after consultation with the Global Patient Safety Physician has reviewed the AEs of interest and identified which higher-level terms and which preferred terms contribute to each AESI. Further reviews may take place prior to database lock (DBL) to ensure any further terms not already included are captured within the categories.

3.3.4 Analysis of Total Calcium per NCI CTCAE criteria

As applicable, values will be converted to standard units and will be graded using CTCAE version referenced in the Clinical Study Protocol. Corrected calcium records will be programmatically derived from Total Calcium and Albumin and appended to the lab dataset for grading.

3.4 Pharmacokinetic Variables

The following PK concentrations will be summarised for savolitinib, osimertinib and their metabolites:

- After single dosing: C_{1h} and C_{3h} post-dose.
- After multiple dosing: $C_{pre-dose}$, and at C_{1h} , and C_{3h} , post-dose at Cycle 2 and at pre-dose, 1, 3, 4 and 6 hours post-dose at Cycle 3 Day 1 and pre-dose at Cycle 6 Day 1.

Appropriate PK parameters such as AUC_{ss} , C_{ssmax} , T_{ssmax} , CL_{ss}/F at Cycle 3, Day 1 may also be calculated for savolitinib, osimertinib and their metabolites using non-compartmental analysis.

Pharmacokinetic concentration data will be collected and summarised as per the protocol using nominal sampling times. If calculated, appropriate PK parameters may be reported in the CSR.

3.5 Biomarker Variables

3.5.1 Secondary Variables

Circulating-tumour DNA changes will be evaluated as a surrogate marker of clinical efficacy.

The percentage change in EGFR mutation ctDNA allele frequencies at Week 6 and at other timepoints will be obtained for each patient taking the difference between the allele frequency of EGFR sensitising mutations in ctDNA at Week 6 and the ctDNA at baseline divided by the allele frequency of EGFR sensitising mutations in ctDNA at baseline multiplied by one hundred (i.e., $[\text{Week 6} - \text{baseline}]/\text{baseline} \times 100$). Patients with undetectable EGFR mutations at

baseline will be excluded from this analysis. Samples with undetectable EGFR mutations at Week 6 will be interpreted as 0% allele frequency so that the percentage change is 100%.

The absolute change in ctDNA at Week 6 and over time will be obtained for each patient by the difference between the EGFR mutation ctDNA allele frequencies at timepoint and at baseline.

Patients with detectable EGFR mutations at baseline and available data at 6 weeks will also be categorised into the following groups of ctDNA status: (1) ctDNA clearance: defined by a 100% percent change in EGFR mutations in ctDNA (i.e., undetectable at Week 6) and (2) ctDNA non-clearance: defined by a percent change in EGFR mutations in ctDNA less than 100% (i.e., detectable at Week 6). Patients with undetectable EGFR mutations at baseline will be categorised as “uninformative”.

3.5.2

CCI

CCI

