In general, for efficacy endpoints the last observed measurement prior to randomisation will be considered the baseline measurement. However, if an evaluable assessment is only available after randomisation but before the first dose of randomised treatment then this assessment will be used as baseline. For safety endpoints the last observation before the first dose of study treatment will be considered the baseline measurement unless otherwise specified. For assessments on the day of first dose where time is not captured, a nominal pre-dose indicator, if available, will serve as sufficient evidence that the assessment occurred prior to first dose.

Assessments on the day of the first dose where neither time nor a nominal pre-dose indicator are captured will be considered prior to the first dose if such procedures are required by the protocol to be conducted before the first dose.

In all summaries change from baseline variables will be calculated as the post-treatment value minus the value at baseline. The percentage change from baseline will be calculated as $(\text{post-baseline value} - \text{baseline value}) / \text{baseline value} \times 100$. For any variable subjected to log transformation, the change from baseline calculated and summarised on the log scale will be back-transformed and presented as a ‘baseline scaled ratio’ (BSR). Percentage change will then be calculated as $(\text{BSR} - 1) \times 100$.

Efficacy data will be summarised and analysed based upon the FAS. Safety and treatment exposure data will be summarised based upon the safety analysis set. Study population and demography data will be summarised based upon the FAS. PK data will be summarised based upon the PK analysis set. Summaries will be repeated for the cross-over analysis set as applicable.

The stratification in the statistical analyses will be based on the values entered in the interactive web response system (IWRS) at randomisation, even if it is subsequently discovered that these values were incorrect.

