6 CHANGES OF ANALYSIS FROM PROTOCOL

The formula given in Section 3.5 for the percentage change in EGFR mutation ctDNA allele frequencies at week 6 and other time points will be $[\text{Week 6} - \text{baseline}] / \text{baseline} \times 100$, contrary to Section 9.4.5 of the CSP V3 which states it will be $[\text{Week 6 baseline}] / \text{baseline} \times 100$.

Previous versions of the SAP included comparative inferential analyses; however, since the SAP v2.0 update, it has been decided to remove all such analyses due to the lower than planned sample size following the CSP v3.0 amendment, with the exception of PFS and OS if there are at least 20 events. Where a comparative analysis was planned, summaries by treatment group will still be presented.

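### SAP Section 3.5.1 gives the Week 6 ctDNA percentage change for an undetectable sample the wrong sign for its own formula, so the numeric clearance cut-offs do not match the definitions in words

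*SAP*

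**What the plan says.** SAP Section 3.5.1 computes the ctDNA percentage change as the Week 6 allele frequency minus the baseline allele frequency, divided by baseline, times 100. Patients with no detectable EGFR mutation at baseline are left out of this calculation.

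For samples that become undetectable, the section says: "Samples with undetectable EGFR mutations at Week 6 will be interpreted as 0% allele frequency so that the percentage change is 100" per cent.

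Patients with a detectable baseline and Week 6 data are then put into two groups:

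- "ctDNA clearance: defined by a 100% percent change in EGFR mutations in ctDNA (i.e., undetectable at Week 6")
- "ctDNA non-clearance: defined by a percent change in EGFR mutations in ctDNA less than 100% (i.e., detectable at Week 6")

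Two other sections fix the direction of the change:

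- Section 4.1 sets it for the whole SAP: "In all summaries change from baseline variables will be calculated as the post-treatment value minus the value at baseline".
- Section 6 returns to the ctDNA formula, beginning "The formula given in Section 3.5 for the percentage change in EGFR mutation ctDNA allele frequencies at week 6 and other time points will be", and restates it as Week 6 minus baseline over baseline, to correct the protocol's version.

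Section 4.2.9 uses both variables. It reports descriptive statistics and a waterfall plot of the Week 6 percentage change, and the number and percentage of patients with clearance and non-clearance. Table 1 in Section 1.1 lists the prevalence of ctDNA clearance as a secondary objective.

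**The concern.** The formula yields a signed change: a fall is negative and a rise is positive. The sentence on undetectable samples and the two cut-offs are worded as if the variable were a percentage reduction, where complete loss is +100% and anything less is below 100%. Section 3.5.1 therefore holds two incompatible scales for one variable.

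Two outputs are exposed:

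- **The clearance proportion.** Each group has a numeric rule and a rule in words, and under the formula the two rules disagree.
- **The continuous Week 6 percentage change.** The text states a value of 100% for cleared samples, and no bracketed wording corrects its sign.

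**Working it through.** **Inputs (all from the SAP).**

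- Formula: change = (w - b)/b × 100, with b the baseline and w the Week 6 allele frequency (Sections 3.5.1 and 6; same direction as Section 4.1).
- Undetectable at Week 6: w = 0 (Section 3.5.1).
- b > 0, because undetectable baselines are excluded from the percentage change and classed as uninformative (Section 3.5.1).
- Numeric rules: clearance if change = 100; non-clearance if change < 100 (Section 3.5.1).
- Rules in words: clearance if undetectable at Week 6; non-clearance if detectable (Section 3.5.1).

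**Step 1: try to reproduce the stated 100%.** With w = 0, (0 - b)/b × 100 = -100 for any b > 0. The stated figure is not reproduced. It appears only with the reversed formula, (b - 0)/b × 100 = +100, which the SAP does not use.

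**Step 2: apply both sets of rules.** The baseline of 5% is illustrative; the percentage change depends only on the ratio w/b.

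| Week 6 | Change by formula | Numeric rule | Rule in words |
|---|---|---|---|
| 0% (undetectable) | (0 - 5)/5 × 100 = -100% | non-clearance | clearance |
| 2.5% | (2.5 - 5)/5 × 100 = -50% | non-clearance | non-clearance |
| 5% | (5 - 5)/5 × 100 = 0% | non-clearance | non-clearance |
| 10% | (10 - 5)/5 × 100 = +100% | clearance | non-clearance |
| 12% | (12 - 5)/5 × 100 = +140% | neither | non-clearance |

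The two sets disagree for cleared patients, for an exact doubling and for any rise beyond a doubling. They agree for every detectable value below a doubling.

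**Step 3: is this a minus sign lost in reading the PDF?** No. The minus is present in the formula in both Section 3.5.1 and Section 6. Putting one into the cut-offs would make non-clearance a change below -100%, which cannot occur because an allele frequency cannot be negative. The direction of the inequality would have to change as well.

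**Step 4: effect on the continuous summaries.** Take four patients with assumed values: two cleared, one at -50%, one at +20%.

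- Formula throughout: mean = (-100 - 100 - 50 + 20)/4 = -57.5%; median = (-100 - 50)/2 = -75%.
- Cleared samples entered as +100%, the others by formula: mean = (100 + 100 - 50 + 20)/4 = +42.5%; median = (20 + 100)/2 = +60%.

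In the second case the waterfall plot would draw the two complete clearances as doublings.

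**Step 5: check the repair.** With clearance at a change of -100% and non-clearance above -100%, the five rows of the table become clearance, then non-clearance four times. This matches the rules in words in every row.

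**The case against.** The strongest defence is that the intended groups are plain. The bracketed words name undetectable and detectable at Week 6. With a detectable baseline required, these two groups are exhaustive and mutually exclusive, and they do not depend on any sign. A programmer who follows them makes no error. One who takes the sentence on undetectable samples literally, enters 100% and then tests for 100% also puts cleared patients into the clearance group. That defence stands for the clearance proportion in cleared patients.

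A reader might infer from the numeric rule that every cleared patient will be misclassified and that reported clearance will be about 0% in both arms. The SAP does not support that as a forecast. It requires the programmer to compute -100% from the formula, apply the 100% cut-off to it, and disregard both the sentence assigning 100% and the bracketed definitions. An exact doubling is also an unlikely value for a continuous measurement; a rise beyond a doubling, left without a numeric category, is the less contrived case.

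The stakes are limited too. Section 4.2.9 is descriptive, Section 4.2.1 plans no inferential analyses, and Section 6 keeps comparative analysis only for PFS and OS with at least 20 events. No decision rule depends on this cut-off.

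The defence does not reach the percentage change itself. The bracketed words define groups, not values. The literal route that rescues the clearance count, entering +100% for cleared samples, is the one that distorts the mean, median and waterfall plot.

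**Conclusion.** Section 3.5.1 is wrong as written. Its formula gives -100% for an undetectable Week 6 sample where the text states 100%, and both numeric cut-offs inherit the error. This rests only on the SAP's formula and a baseline above zero.

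The consequences depend on how the text is programmed:

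- Numeric cut-offs on the formula's output: cleared patients go to non-clearance, an exact doubling goes to clearance, and larger rises go unclassified.
- Bracketed words: classification is correct.
- +100% entered for cleared samples and the formula used for the rest: the Week 6 summaries and waterfall plot carry the wrong sign for exactly the patients who cleared.

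How many patients would be affected cannot be known from the SAP. Because recruitment stopped early and the planned sample size will not be met (Section 1.3), a few wrongly signed values could visibly move a mean or median. The endpoint is secondary and descriptive, so this is a definition to correct rather than a threat to the trial's main conclusions.

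**What to change.** In Section 3.5.1:

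- State that an undetectable Week 6 sample is taken as 0% allele frequency, so that the percentage change is -100%.
- Define clearance as detectable at baseline and undetectable at Week 6 (change = -100%).
- Define non-clearance as detectable at baseline and detectable at Week 6 (change > -100%, including any increase).

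Sections 4.1 and 6 can stay as they are, since they already agree with the formula. Keeping the 100% cut-offs and switching to a percentage reduction would classify patients identically, but it would contradict the formula in Sections 3.5.1 and 6 and the direction set in Section 4.1, so it is the poorer choice.

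The cost is a few words and signs in one section and a check that the programming follows them. It needs no new data and no change to the design.

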4 ANALYSIS METHODS

4.1 General Principles

The below mentioned general principles will be followed throughout the study:

- Descriptive statistics will be used for all variables, as appropriate. Continuous variables will be summarised by the number of observations, mean, standard

deviation, median, upper and lower quartiles minimum, and maximum. For log-transformed data it is more appropriate to present geometric mean, coefficient of variation (CV), median, minimum and maximum. Categorical variables will be summarised by frequency counts and percentages for each category.

- Unless otherwise stated, percentages will be calculated out of the population total for the corresponding treatment group. Overall totals will be calculated for baseline summaries only.
- For continuous data, the mean and median will be rounded to 1 additional decimal place compared to the original data. The standard deviation will be rounded to 2 additional decimal places compared to the original data. Minimum and maximum will be displayed with the same accuracy as the original data.
- For categorical data, percentages will be rounded to 1 decimal place.
- SAS® version 9.4 or higher will be used for all analyses.
- There are three MET amplification and/ or overexpression biomarker groups of analytical interest as follows:
 - All patients: This population includes all randomised patients.
 - FISH10+ patients: This population includes patients who meet the high biomarker cut-off for FISH as defined in Section 3.5.
 - CCI patients: This population includes patients who meet the high biomarker cut-off for CCI as defined in Section 3.5.

These groups are not mutually exclusive, i.e. a patient may be a member of all three groups.

- Unless otherwise specified, analyses will be presented by treatment group and biomarker group (FISH10+, CCI, FISH10+ and/or CCI, and all patients).
- Additional combinations of line of therapy and biomarker group may be further investigated.

In general, for efficacy endpoints the last observed measurement prior to randomisation will be considered the baseline measurement. However, if an evaluable assessment is only available after randomisation but before the first dose of randomised treatment then this assessment will be used as baseline. For safety endpoints the last observation before the first dose of study treatment will be considered the baseline measurement unless otherwise specified. For assessments on the day of first dose where time is not captured, a nominal pre-dose indicator, if available, will serve as sufficient evidence that the assessment occurred prior to first dose.

Assessments on the day of the first dose where neither time nor a nominal pre-dose indicator are captured will be considered prior to the first dose if such procedures are required by the protocol to be conducted before the first dose.

In all summaries change from baseline variables will be calculated as the post-treatment value minus the value at baseline. The percentage change from baseline will be calculated as $(\text{post-baseline value} - \text{baseline value}) / \text{baseline value} \times 100$. For any variable subjected to log transformation, the change from baseline calculated and summarised on the log scale will be back-transformed and presented as a ‘baseline scaled ratio’ (BSR). Percentage change will then be calculated as $(\text{BSR} - 1) \times 100$.

Efficacy data will be summarised and analysed based upon the FAS. Safety and treatment exposure data will be summarised based upon the safety analysis set. Study population and demography data will be summarised based upon the FAS. PK data will be summarised based upon the PK analysis set. Summaries will be repeated for the cross-over analysis set as applicable.

The stratification in the statistical analyses will be based on the values entered in the interactive web response system (IWRS) at randomisation, even if it is subsequently discovered that these values were incorrect.

4.2 Analysis Methods

4.2.1 Multiplicity

There will be no adjustment for multiplicity as **CCI**, and no inferential analyses are planned.

4.2.2 Primary Efficacy Endpoint

4.2.2.1 Objective response rate (ORR)

The ORR will be based on the site investigator RECIST data, and using all scans regardless of whether they were scheduled or not. The ORR will be summarised by n (%) in each treatment arm.

Summaries by treatment group will be produced that present the number and percentage of patients with a tumour response (CR/PR) based upon the number of patients with measurable disease at baseline per the site investigator. The response rates by treatment group will be presented with a 2-sided 95% CI using the Clopper-Pearson method.

This analysis of ORR will be repeated for second line patients (i.e. patients with one prior line of therapy before the study treatment).

These summaries will also be produced for ORR per BICR (based upon the number of patients with measurable disease at baseline per BICR). If there is an important discrepancy between the primary analysis using the site investigator data and this sensitivity analysis using BICR data then the proportion of patients with site but no central confirmation of progression will be

summarised; such patients have the potential to induce bias in the central review due to informative censoring. Disagreements between investigator and central reviews of RECIST progression will be presented for each treatment group.

Additionally, a summary of ORR in the first 10 monotherapy arm patients who have had the opportunity to be treated for two RECIST post-baseline scans (12 weeks, the Monotherapy Analysis Set) will be performed. This summary will have no impact on the CoC study and will only be used for exploratory purposes. The first 10 randomised patients will be selected from the savolitinib plus placebo arm, after first excluding any randomised patients who were accidentally unblinded.

For each treatment group best objective response (BoR) will be summarised by n (%) for each category (CR, PR, SD, PD and NE) based upon the FAS. This analysis will be repeated for second line patients (i.e. patients with one prior line of therapy before the study treatment).

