1.1 Study Objectives

The study objectives and the corresponding endpoints/variables are shown in Table 1.

Table 1 Study objectives and corresponding endpoints/variables

Primary objective:	Primary endpoints/variables:
To assess the ORR of savolitinib in combination with osimertinib versus savolitinib in combination with placebo in patients with EGFRm+, MET amplified locally advanced or metastatic NSCLC who have progressed on previous osimertinib therapy.	Objective response rate is defined as the proportion of patients with measurable disease who have a CR or PR as determined by the investigator at the local site per RECIST 1.1.
Secondary objectives:	Secondary endpoints/variables:
To determine the efficacy of savolitinib in combination with osimertinib versus savolitinib in combination with placebo in patients with EGFRm+, MET amplified locally advanced or metastatic NSCLC who have progressed on previous osimertinib therapy.	
 • Progression-free survival is defined as time from randomisation until progression per RECIST 1.1 as assessed by the investigator or death due to any cause. • Duration of response is defined as the time from the date of first documented response until date of documented progression per RECIST 1.1 as assessed by the investigator or death in the absence of disease progression. • Tumour size assessment is defined as the percentage change from baseline in TLs at 12 weeks per RECIST 1.1 as assessed by the investigator. • Overall survival is defined as time from randomisation until the date of death due to any cause.

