1.2 Study Design

This is a multi-centre, Phase II, double-blind, randomised study designed to determine the efficacy of savolitinib administered orally in combination with osimertinib versus savolitinib in combination with placebo in patients with EGFRm+, MET amplified, locally advanced or metastatic NSCLC who have progressed on previous osimertinib treatment.

Prior to CSP Version 3.0, approximately 56 patients were planned to be randomised in a ratio of 1:1 to receive treatment with CCI savolitinib once daily plus CCI osimertinib once daily, or CCI savolitinib once daily plus placebo. At least half of the patients randomised into the study will be second line patients who were treated with osimertinib as first line therapy. Randomisation will be stratified according to the number of prior lines of therapy (i.e., osimertinib monotherapy as first line or \geq second line [which includes patients who received osimertinib monotherapy before or after chemotherapy]).

Prospective testing of tumour specimens to determine MET amplification by central fluorescence in situ hybridisation (FISH) using tumour specimens collected after progression on prior treatment with osimertinib should be performed at Pre-screening in advance of Screening. Patients determined to be MET amplified in Pre-screening will undergo screening during the 28 days prior to randomisation to confirm eligibility.

All patients confirmed as eligible will begin treatment on Day 1 with savolitinib plus osimertinib or savolitinib plus placebo. Treatment will continue once daily in 28-day cycles until either

objective PD by RECIST 1.1 is assessed, unacceptable toxicity occurs, consent is withdrawn, or another discontinuation criterion is met. Patients randomised to the savolitinib plus placebo arm may cross-over to open-label savolitinib plus osimertinib following investigator-assessed objective PD to ensure that all patients enrolled may have the opportunity to receive the combination of savolitinib plus osimertinib.

A non-comparative interim futility analysis for the savolitinib plus placebo arm was planned to occur after 20 patients overall (10 per arm) had the opportunity of being treated for 2 RECIST post-baseline scans (12 weeks). Recruitment was to continue during this interim futility analysis.

[figure not shown]
Randomised study design, cross-over study design and end of study design are described in the CSP Section 4.1.

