1.3 Number of patients

Prior to CSP V3.0, the treatment of approximately 56 patients (28 per arm) with EGFRm+ and MET amplified locally advanced or metastatic NSCLC who have progressed following treatment with osimertinib was considered adequate for this study. CCI

At least half of the patients planned to be randomised into the study will be second-line patients who were treated with osimertinib as first-line therapy.

Under CSP V3.0, the planned number of randomised patients will not be met. This is a result of the decision by AstraZeneca to terminate study recruitment early.

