4.2.2.1.1 Subgroup analyses

Subgroup analyses will be conducted, summarising ORR in the treatment groups in the following subgroups of the FAS:

- Prior lines of therapy (osimertinib monotherapy as first line versus \geq second line)
- FISH allocation status (amplified versus polysomy, or missing).

The subgroups for prior lines of therapy will be determined by the values entered into the IWRS at randomisation, even if it is subsequently discovered that these values were incorrect.

All patients randomised in the study will be MET amplified (FISH+). The FISH allocation status of amplification is considered a ratio of 'Mean MET/CEP7 RATIO' ≥ 2 , and polysomy where this ratio < 2 . If the ratio variable is missing, patients will be presented in a missing category.

The purpose of the subgroup analyses is to assess the consistency of treatment effect across expected prognostic and/or predictive factors. These subgroup analyses will be repeated for the FISH10+ biomarker group and for the **CCI** biomarker group.

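### The primary objective compares ORR between randomised arms, but the SAP prespecifies no between-arm ORR contrast or interval, only per-arm rates

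*SAP*

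**What the plan says.** Section 1.1, Table 1, states the primary objective as a contrast: "To assess the ORR of savolitinib in combination with osimertinib versus savolitinib in combination with placebo". Section 1.2 describes a double-blind study in which patients were "planned to be randomised in a ratio of 1:1".

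Section 4.2.2.1 sets out the ORR analysis: "The ORR will be summarised by n (%) in each treatment arm", and "The response rates by treatment group will be presented with a 2-sided 95% CI using the Clopper-Pearson method". The same per-arm summaries are repeated for second-line patients and for BICR. No between-arm measure of ORR appears there or elsewhere in the current text.

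Section 4.2.2.1.1 says the ORR subgroup summaries are meant to "assess the consistency of treatment effect across expected prognostic and/or predictive factors".

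Section 6 records that comparative inferential analyses were taken out because the sample is smaller than planned, "with the exception of PFS and OS if there are at least 20 events", and that per-arm summaries stand in where a comparison had been planned. Section 4.2.1 says no inferential analyses are planned. Section 4.2.3.1 keeps a stratified Cox hazard ratio with 95% CI for PFS once there are at least 20 events, and Section 4.2.3.3 carries this over to OS.

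On size, Section 1.3 gives the former target as "approximately 56 patients (28 per arm") and says that "the planned number of randomised patients will not be met". Section 1.2 says the planned primary analysis will not be performed. A final analysis follows nine months after the last randomisation.

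**The concern.** The objective asks how much ORR differs between randomised arms, and the analysis answers a different question: what the rate is in each arm. Two secondary endpoints keep a between-arm estimate with an interval, subject to an event count, while the primary endpoint has none. The subgroup section then refers to the consistency of an effect for which no ORR measure has been defined, so as written its stated purpose cannot be met.

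What is at stake is prespecification. If a difference is wanted in the study report, the effect measure, the interval method and the handling of the prior-lines stratum would be chosen after unblinding. If none is reported, a reader has only two separate intervals to set side by side, and overlap of separate 95% intervals is a conservative guide to the difference.

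**Working it through.** **The plan's own figure.** 2 × 28 = 56 agrees with Section 1.3. The rates, alpha and power behind it are not visible (the text is redacted), so the target cannot be rebuilt. The point does not depend on it.

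**What each endpoint gets.**

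| Endpoint | Per-arm summary | Between-arm estimate with CI |
|---|---|---|
| ORR (primary) | n (%), Clopper-Pearson 95% CI | none |
| PFS (secondary) | Kaplan-Meier summaries | HR, 95% CI, if at least 20 events |
| OS (secondary) | Kaplan-Meier summaries | HR, 95% CI, if at least 20 events |

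**Precision the SAP already accepts.** With 1:1 allocation and d events, SE(log HR) is about √(4/d), ignoring stratification. At d = 20 this is √0.2 = 0.447, and exp(1.96 × 0.447) = 2.40. The 95% CI therefore runs from about HR/2.4 to HR × 2.4.

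**What an ORR difference would look like.** The document gives no final sample size and no response rates, so every count below is an assumption. The Newcombe hybrid-score interval uses the Wilson limits (l, u) of each arm:

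- lower = d − √[(p₁ − l₁)² + (u₂ − p₂)²]
- upper = d + √[(u₁ − p₁)² + (p₂ − l₂)²]

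For 9/15 v 3/15, p₁ = 60% with Wilson limits 35.75 to 80.18, p₂ = 20% with Wilson limits 7.05 to 45.19, and d = 40 points.

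- lower = 40 − √(24.25² + 25.19²) = 40 − 34.97 = 5.0
- upper = 40 + √(20.18² + 12.95²) = 40 + 23.98 = 64.0

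| Assumed counts | Clopper-Pearson per arm (%) | Difference (points) | Newcombe 95% CI | Fisher two-sided p |
|---|---|---|---|---|
| 6/10 v 2/10 | 26.2–87.8; 2.5–55.6 | 40.0 | −2.3 to 67.3 | 0.17 |
| 8/15 v 3/15 | 26.6–78.7; 4.3–48.1 | 33.3 | −0.9 to 58.7 | 0.13 |
| 9/15 v 3/15 | 32.3–83.7; 4.3–48.1 | 40.0 | 5.0 to 64.0 | 0.060 |
| 12/20 v 5/20 | 36.1–80.9; 8.7–49.1 | 35.0 | 4.4 to 57.8 | 0.054 |
| 17/28 v 6/28 | 40.6–78.5; 8.3–41.0 | 39.3 | 13.5 to 58.6 | 0.006 |

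The table shows three things. A difference with an interval can be computed at every size tried. It is wide. The per-arm intervals overlap in all five rows, including the last, where both the score interval and the exact test point to a difference. In the 9/15 and 12/20 rows, the score interval excludes 0 while Fisher's test does not reach 5%. One responder fewer at 15 per arm (8 instead of 9) moves the lower limit below 0. That sensitivity is a reason to name the method in advance.

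**The case against.** The strongest reply is that this is a disclosed decision and not an oversight. Recruitment stopped early, Section 1.2 cancels the planned primary analysis, Section 4.2.1 declares no inferential analyses, and Section 6 gives both the reason and the replacement. Table 1 keeps the objectives and Section 6 records the departure from them. All of that stands, and the point must not be presented as an unexplained gap.

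Second, the counts, denominators and exact intervals are reported for both arms, by investigator and by BICR. The difference is one subtraction, and any unstratified interval follows from the counts. A hazard ratio cannot be recovered from per-arm medians in that way, which is a practical reason for treating PFS and OS differently, and the hazard ratio is itself conditional on 20 events. This also stands. It weakens the inconsistency between endpoints but does not remove it, because a contrast recovered by the reader has no prespecified measure or method.

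Third, the SAP nowhere says the arms will be compared by overlap of intervals, so that misuse is a risk and not something planned.

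A reader might infer that the trial never estimates its primary quantity, or that no valid statement of precision is available. The document does not support either reading. Each arm has a valid exact interval, and the point difference can be recovered. A reader might also take the illustration to show that the per-arm display would hide a real effect. It cannot show that, because the counts are assumed and the result turns on method and counts.

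**Conclusion.** The point holds as a mismatch between objective and analysis: a randomised ORR comparison is the stated aim, and no between-arm ORR contrast or interval is prespecified. The reason given in Section 6 covers dropping a test. It does not cover dropping a descriptive estimate, since the SAP accepts an HR whose 95% limits lie a factor of about 2.4 either side of the estimate for PFS and OS. The purpose stated for the ORR subgroup summaries also needs an effect measure that the SAP does not define.

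The consequence is moderate. No information is lost, and the study makes no inferential claim. This is a change that should be made because it is cheap and lets the report answer its own question; it does not invalidate the plan. The conclusion rests on the text alone. The numerical examples rest on assumed sizes and counts, and redacted text is not held against the plan.

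**What to change.** Add to Section 4.2.2.1: *The difference in ORR (savolitinib plus osimertinib minus savolitinib plus placebo) will be presented with a two-sided 95% CI by the Newcombe hybrid-score method, unstratified because of the small sample. It is descriptive and no p-value will be given.* Apply it to investigator ORR and to BICR ORR, each with its own measurable-disease denominator.

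Then align the other sections:

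- Section 6: list ORR beside PFS and OS as an exception.
- Section 4.2.1: state that the between-arm estimates for ORR, PFS and OS are descriptive.
- Section 4.2.2.1.1: either name the ORR difference as the measure whose consistency is looked at, or describe the subgroup output as per-arm summaries only.

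If the sponsor wants no contrast at all, the mismatch can be closed instead by stating that the ORR analysis is descriptive per arm and removing the reference to a treatment effect from the subgroup section.

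The cost is a few lines of SAP text and one row per ORR table. The downside is a wide interval that must be labelled descriptive, so that exclusion or inclusion of 0 is not read as a test.
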